## 9.2 SAMPLE SIZE DETERMINATION

The sample size calculation is for the primary hypothesis. A total of 32 participants (Groups 1-3) provides non-overlapping 95% confidence intervals to detect an increase of at least 3.5% in the research CBCT ICC compared to a standard CBCT ICC of 0.95. We expect a high-level agreement for the standard CBCT method but if the ICC for the standard CBCT is slightly lower at 0.9 or even 0.8 we are still able to detect an increase in the research CBCT of at least 7.7% and 17%, respectively [34].

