For each participant and CBCT modality an average delineation will be determined using the STAPLE algorithm. This average delineation will be used as the reference delineation to compute four pairwise CIs between the reference and each observer. This pairwise approach to determine the CIs was chosen over the generalized conformity index since it can be used to account for variability among the observers, which in turn will improve our ability to compare the two imaging modalities. A two-way random effects model (random effects for participant and observer) will be carried out for each modality to calculate the ICC and its 95% confidence interval using bootstrapping for absolute agreement. The ICC will be calculated using the form ICC(2,k) so that the results can be generalized to any observer with a similar skill set. If the 95% confidence interval of ICC does not overlap between the two modalities, we will conclude they are significantly different at a 0.05 significant level. We will also examine whether anatomical location impacts performance through subgroup analyses on Groups 1-3.

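### Section 9.2 gives no probability for the ICC increases it says 32 participants can detect; under the planned non-overlap rule each would be detected only about half the time.

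*Combined protocol and SAP*

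**What the plan says.** Section 9.2 describes its calculation as being for the primary hypothesis. For Groups 1–3 it claims that a sample of 32 "provides non-overlapping 95% confidence intervals to detect an increase of at least 3.5% in the research CBCT ICC compared to a standard CBCT ICC", taking the standard value to be 0.95. It then turns to lower standard values ("if the ICC for the standard CBCT is slightly lower at 0.9 or even 0.8") and says of these that "we are still able to detect an increase in the research CBCT of at least 7.7% and 17%, respectively". No power or other probability of detection appears there, nor does the number of observers, the ICC form or the interval method. The only source cited is the sample-size software.

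The matching decision rule is in Section 9.4.7: "If the 95% confidence interval of ICC does not overlap between the two modalities, we will conclude they are significantly different", with the level given as 0.05. That section also specifies ICC(2,k), bootstrap 95% intervals, and four observers per scan ("This average delineation will be used as the reference delineation to compute four pairwise CIs between the reference and each observer", where the abbreviation means conformity indexes).

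Under Sections 3, 9.1 and 9.4.2 the primary endpoint is now CT number error, artifact amplitude and contrast-to-noise ratio. The observer ICC comparison is one of several candidate exploratory analyses. Section 9.4.3 also names the ICC as a reliability metric for the secondary endpoint, but attaches no decision rule to it.

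**The concern.** A reader who meets *provides* and *able to detect* in a sample-size section will assume conventional power, usually 80% or 90%. If the figures are only the points at which two expected intervals stop overlapping, they carry no allowance for sampling error in the two estimated ICCs. The study would then miss a real increase of the stated size about as often as it found one.

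These are the only figures offered in support of n=32. If the ICC analysis is run and the intervals overlap, Section 9.2 as worded invites the inference that increases of this size are unlikely. The design would not support that inference.

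**Working it through.** **Inputs.** From Section 9.2: n = 32; standard ICCs r₁ = 0.95, 0.90, 0.80; increases 3.5%, 7.7%, 17%. Read as relative increases, the research ICCs are r₂ = 0.98325, 0.9693, 0.936. From Section 9.4.7: k = 4 observers, average-measure ICC, non-overlap of two 95% intervals. Assumed here: normal scores, no observer variance and F-based intervals in the main calculation, and the two scans' ICC estimates independent unless stated.

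**Step 1: reproduce the printed figures.** For an average-measure ICC, F = 1/(1 − ICC), with n − 1 = 31 and (n − 1)(k − 1) = 93 degrees of freedom. The 95% limits are

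- lower = 1 − a/F, with a = F₀.₉₇₅(31, 93) = 1.717
- upper = 1 − 1/(bF), with b = F₀.₉₇₅(93, 31) = 1.870

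Setting the upper limit for r₁ equal to the lower limit for r₂ gives (1 − r₁)/(1 − r₂) = ab = 3.211, so r₂ = 1 − (1 − r₁)/3.211.

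| r₁ | touching r₂ | increase at touch | printed increase | upper limit for r₁ | lower limit for printed r₂ |
|---|---|---|---|---|---|
| 0.95 | 0.9844 | 3.62% | 3.5% | 0.9733 | 0.9712 |
| 0.90 | 0.9689 | 7.65% | 7.7% | 0.9465 | 0.9473 |
| 0.80 | 0.9377 | 17.2% | 17% | 0.8931 | 0.8901 |

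A single-measure ICC with k = 3 gives 3.70%, 7.73% and 16.99%; with k = 4 it gives 3.58%, 7.46% and 16.32%. No configuration tried hits all three printed figures exactly as relative increases, but these forms place them near the touching point.

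**Step 2: probability of non-overlap at the printed increases.** The research interval lies above the standard one when the ratio of observed F values exceeds 3.211. Each observed F is an F(31, 93) variate divided by (1 − r). The condition is therefore that the ratio of two independent F(31, 93) variates exceeds 3.211 × (1 − r₂)/(1 − r₁):

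- 0.95: 3.211 × 0.01675/0.05 = 1.08
- 0.90: 3.211 × 0.0307/0.10 = 0.99
- 0.80: 3.211 × 0.064/0.20 = 1.03

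That ratio has median 1, so the chance must be near one half. Simulation gives:

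| Setting (n = 32) | 0.95 | 0.90 | 0.80 |
|---|---|---|---|
| Average-measure, k = 4, F-based, independent | 43% | 51% | 47% |
| Same, between-scan correlation 0.5 | 42% | 51% | 47% |
| ICC(2,k), percentile bootstrap, correlation 0.5 | 50% | 60% | 53% |
| Single-measure, k = 4, independent | 46% | 57% | 58% |
| Single-measure, k = 3, independent | 39% | 49% | 50% |

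At a between-scan correlation of 0.9 the F-based results widen to 34–68%. No variant reaches 80% at the printed relative increases.

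**Step 3: how much is due to the rule.** With equal ICCs and independent scans, the ratio falls outside 1/3.211 to 3.211 in about 0.6% of trials, and in fewer when the scans are correlated. A genuine two-sided 5% comparison needs a ratio of only about 2.28. At that threshold, power for the printed increases is about 74%, 80% and 77% with independent scans. Across correlations from 0 to 0.9 it is 73–97%, 81–98% and 78–94%.

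**Step 4: increases detectable with 80% probability under the non-overlap rule.** The true ratio (1 − r₁)/(1 − r₂) must be about 4.56, so r₂ = 1 − (1 − r₁)/4.56:

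- 0.95: r₂ = 0.989, an increase of 4.1%
- 0.90: r₂ = 0.978, an increase of 8.7%
- 0.80: r₂ = 0.956, an increase of 19.5%

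With bootstrap ICC(2,k) intervals the detection probability at these values is 81–86%, so the bootstrap figures for 80% would be slightly smaller.

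**The case against.** Four arguments carry weight.

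*The rule is the cause.* The shortfall comes largely from a rule far stricter than its stated level. At a true 5% level the printed increases are detected with roughly conventional power. This stands, and it makes the point conditional on the non-overlap rule. A reader might infer that the shortfall is independent of the rule's level; Step 3 shows that it is not.

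*The method is inferred.* Section 9.2 gives no k, ICC form or interval type. This also stands. A reader might go further and say that 3.5% fails even on its own terms because the touching point is 3.62%. The documents do not support that: the gap depends on inputs borrowed from Section 9.4.7 and on F-based intervals the plan does not use, and the bootstrap gives about 50% in that case. Nor can it be said that the figures could have arisen in no other way. If the increases were absolute points, the probabilities would be about 53%, 76% and 96%, but that reading does not reproduce the set of three at n = 32 and k = 4.

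*The ICC comparison is now exploratory, and Section 9.2 sizes a former endpoint.* This is correct and lowers the importance. It does not make the stated property true, and no other justification for n = 32 is given.

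*Section 9.2 never mentions power, and sizing a pilot by interval separation is a recognisable precision criterion.* This stands in part. But the text names detectable increases rather than interval widths, and Section 9.4.7 turns non-overlap into a significance claim. No passage says that an overlapping result would rule these increases out; that is a risk of misreading, not a stated plan.

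**Conclusion.** The concern holds in a conditional form. Under the non-overlap rule of Section 9.4.7, increases of 3.5%, 7.7% and 17% would each be detected in about half of trials, roughly 40–60% across the main variants, so the unconditional wording of Section 9.2 claims something the design does not deliver. The result rests on normal scores, relative increases, an assumed between-scan correlation, and an observer number and ICC form taken from Section 9.4.7. The choice among average-measure with k = 4 and single-measure with k = 3 or 4 does not alter the conclusion.

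A reader might also infer that 32 participants are too few. Reaching 80% at the printed increases under the same rule would take about 61, 52 and 56 participants. The documents give no reason to enlarge the study on this account: the comparison is exploratory, and much of the loss comes from the rule.

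**What to change.** Keep n = 32 and revise Section 9.2 in one of two ways:

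- retain the three printed increases and state that each has only about a 50% chance of giving non-overlapping intervals; or
- replace them with increases computed at a stated power under the analysis actually planned. For 80% with the non-overlap rule and F-based intervals these are about 4.1%, 8.7% and 19.5%. They should be recomputed with the planned bootstrap, and again if the rule is replaced by a direct comparison of the two ICCs.

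In either case, remove *provides* and *able to detect* as unconditional claims; state the number of observers, ICC form, interval method and assumed between-scan correlation; and label the calculation as applying to the exploratory ICC comparison, not to the current primary endpoint.

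The cost is a wording change and a short simulation, with no added participants or scans. The stated detection claim becomes somewhat less favourable.

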## 9.3 POPULATION FOR ANALYSES

Data from participants who complete both research and standard clinical CBCT scans, and the scans are evaluable, will be used for primary and secondary analyses. The study intervention is a CBCT scan for observation purposes, without any anticipated adverse effects on the participant. Therefore, safety analysis dataset is not needed in this study.

## 9.4 STATISTICAL ANALYSES

### 9.4.1 GENERAL APPROACH

**Study #1 (Primary objective):** Improvement in tissue visualization and quantitative accuracy will be evaluated comparatively between the CBCT scans acquired with and without the 2D grid. Objective image metrics will be employed to quantify tissue visualization and quantitative accuracy. Three image quality metrics will be extracted from each CBCT scan; absolute CT number error, image artifact amplitude, and contrast to noise ratio (CNR). To calculate CT number errors and artifact amplitude, multiple ROIs will be placed primarily in the soft tissue and adipose sections of the imaged anatomy in coregistered CBCT and simulation CT images. CT number error is defined as the absolute difference in mean HU values between the CBCT and the gold standard CT images of a given ROI. Artifact amplitude is defined as the difference between the maximum and minimum value of CT number errors extracted from ROIs in a given CBCT scan. For CNR calculations paired ROIs will be placed in each imaged volume, such that one of the ROIs in the pair will be placed in soft tissue, and the other will be placed in adipose tissue in proximity of the first ROI. CNR is calculated by using the following:

$$CNR = \frac{|HU_{soft} - HU_{adipose}|}{(\sigma_{soft} + \sigma_{adipose})/2}$$

Where  $HU_{soft}$  and  $HU_{adipose}$  are the mean HU values of soft tissue and adipose tissue ROI pairs.  $\sigma_{soft}$  and  $\sigma_{adipose}$  are the HU standard deviation of soft tissue and adipose tissue ROI pairs. These metrics serve as surrogates that quantify tissue visualization. A statistically significant improvement in these metrics when compared to metrics extracted from standard clinical CBCT scans would indicate that tissue visualization and quantitative accuracy would be potentially improved by CBCT scans with 2D grid.

**Study #2 (Secondary Objective), evaluate the consistency of organ delineation by automated software tools:** Evaluations in study 2 will be similar as those in study 1. The exception is that the pairwise comparisons will consist of comparing the automated software delineation to delineations for each of the four observers. This will allow us to evaluate how consistent the automated delineation is with human delineations, and whether a given imaging modality results in a more consistent automated delineation.

**Study #3 (Exploratory Objective), assess the utility of CBCT images in qualitative and quantitative imaging tasks:** Several studies will be considered for the exploratory analysis.

Improvement of organ or anatomical structure visualization by observers: We hypothesize that anatomical structure visualization can be improved by higher quality CBCT images. To quantify tissue visualization, we will ask multiple observers to delineate organ boundaries. Since the ground truth about organ boundaries cannot be determined from images, we will evaluate the inter-observer agreement among delineated structures. Four observers will delineate a set of anatomical

structures in each helical CT and CBCT scan in a blinded fashion. For each image set, a reference delineation will be determined from delineations of four observers using the STAPLE algorithm. Conformity Indexes (CI) and Hausdorff distances (HD) will be used as metrics of similarity. CI is the ratio of the sum of all overlapping volumes between pairs of observers and the sum of all overlapping and all non-overlapping volumes between the same pairs. HD defined as the maximum distance between the closest points of two delineations. CI of one or HD of 0 mm indicates perfect agreement among observers' delineations. We will have CIs and HDs determined between the reference delineation and each observer. This pairwise approach to determine the CIs can be used to account for variability among the observers, which in turn will improve our ability to compare the two imaging modalities.

To evaluate the consistency of organ delineation by different observers, we will calculate intraclass correlation coefficient (ICC), which is a reliability metric. The ICC is simply the proportion of the total variability in the data that can be attributed to variability between participants. In the context of this study, the ICC is directly related to how well the observer delineations agree, with a higher ICC indicating better agreement. Our aim is to evaluate how ICC varies between standard clinical CBCT and CBCT with 2D grid. We hypothesize that the ICC will be better for CBCT with 2D grid.

Analysis of radiomics feature extraction accuracy: In each image set, we will extract series of radiomics features, such as HU value statistics (e.g. mean, variance, and kurtosis), and texture features, such as gray-level co-occurrence matrix, wavelets, local entropy. Accuracy and repeatability of radiomics features in CBCT (both standard and 2D grid CBCT) and gold standard helical CT will be evaluated using Lin's concordance correlation coefficient (CCC) as in Zhao's work [35]. Statistical analysis details of other potential exploratory studies, such as qualitative and quantitative image quality evaluations, and CBCT-based dose calculations will be determined on an ad hoc basis.

The analysis of TrueBeam (Groups 1-3) and Proteus (Group 4) CBCT images. An image quality difference is expected between TrueBeam and Proteus CBCT due to differences in system design (e.g. TrueBeam has bow tie filter, whereas Proteus does not have one), and image reconstruction chain. Therefore, in the primary analysis, we will analyze the data from patient Groups 1-3 (TrueBeam) and Group 4 (Proteus) separately. This way, we will eliminate potential, system-specific image quality bias. In a subgroup analysis, we will investigate the differences in the study results of Groups 2 and 4 (i.e. prostate cancer patients scanned with TrueBeam and Proteus, respectively).

---

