## 9 STATISTICAL CONSIDERATIONS

### 9.1 STATISTICAL HYPOTHESES

- Primary Efficacy Endpoint:  
The primary endpoint of this study is to evaluate the change in objective image quality metrics in CBCT images acquired with the 2D grid, when compared to CBCT images without the 2D grid. We will place multiple ROIs in each CBCT scan, and calculate absolute CT number error, artifact amplitude, and contrast to noise ratio (CNR). We will evaluate the statistical significance of the differences of these metrics between research CBCT and standard clinical CBCT scans. We hypothesize that CBCT scan with 2D grid will provide significantly lower CT number errors and artifact amplitudes when compared to standard clinical CBCT scans. We also hypothesize that CBCT scans with 2D grid will provide equivalent or better CNR than standard clinical CBCT scans.
- Secondary Efficacy Endpoint(s):
  - 1) We hypothesize that the accuracy of software tools can also be improved in auto-delineation of tissues in CBCT scans. In this case, we will use manual delineations from the observers as the gold standard and measure the similarity of software generated and observer generated delineations by using the CI and HD metrics.

- Tertiary Efficacy Endpoint(s):
  - 1) Assessment of radiomics feature extraction accuracy: We hypothesize that image intensity and texture (radiomics) features are more consistent in higher quality CBCT images. The gold standard consistency of radiomics features is MDCT scans. Thus, we will evaluate the correlation of radiomics features in CBCT scans and MDCT scans, by using the CCC metric. Higher correlation of radiomics features between CBCT and MDCT scans will yield higher CCC values.
  - 2) Assessment of image quality rankings by observers, evaluation of quantitative image quality metrics, and evaluation of dose calculation accuracy. Metrics obtained in each study will be evaluated comparatively. The statistical significance of differences in quality metrics extracted from research and standard clinical CBCT scans will be evaluated.
  - 3) Determine the consistency of organ/tissue delineations across different observers, when using CBCT image sets with better image quality. We will calculate intra-class correlation coefficient (ICC) on CI and HD metrics to measure the effect of standard clinical CBCT and 2D Grid CBCT on organ delineation consistency.

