#### **9.4.2 ANALYSIS OF THE PRIMARY EFFICACY ENDPOINT(S)**

Our primary analysis will evaluate the tissue visualization and quantitative accuracy of CBCT scans with 2D grid, as measured by objective image quality metrics. These metrics, namely absolute CT number error, artifact amplitude, and CNR, will be extracted from research CBCT

and standard clinical CBCT pairs of each study participant. In each CBCT image set, each metric will be measured from multiple ROIs, and their respective average values will be calculated. Subsequently, these values will be log transformed (natural logarithms) for the validity of normality. The Linear Mixed Effects model will be used to evaluate the differences in image quality metrics among CBCT types, while adjusting the random patients effect. The lower and upper limits of the 95% confidence interval will be calculated for each image quality metric and for each CBCT type. Image quality metrics of research CBCT scans and standard clinical CBCT scans will be compared in a pairwise fashion for the statistical significance of the differences between the two CBCT types. In a subgroup analysis, image quality metrics will be stratified into anatomical region groups and patient size groups to assess the effect of anatomical region and patient size on the image quality differences between the two CBCT types.

---

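### Artifact amplitude is one range of absolute errors pooled over soft-tissue and adipose ROIs, so a soft-versus-adipose HU difference between CBCT types can register as a change in artifact

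*Combined protocol and SAP*

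**What the plan says.** Section 9.4.1 (Study #1) sets three steps. The ROIs: "multiple ROIs will be placed primarily in the soft tissue and adipose sections of the imaged anatomy in coregistered CBCT and simulation CT images". The error: "CT number error is defined as the absolute difference in mean HU values between the CBCT and the gold standard CT images", taken for each ROI. The metric: "Artifact amplitude is defined as the difference between the maximum and minimum value of CT number errors extracted from ROIs in a given CBCT scan". ROIs from both tissues therefore enter one range, and the errors in that range are unsigned.

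Section 9.1 attaches a primary hypothesis to the metric: "CBCT scan with 2D grid will provide significantly lower CT number errors and artifact amplitudes when compared to standard clinical CBCT scans". Section 9.4.2 adds that "each metric will be measured from multiple ROIs, and their respective average values will be calculated" and that "these values will be log transformed (natural logarithms) for the validity of normality". A linear mixed model with a random patient effect then compares the CBCT types.

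Nothing elsewhere separates the tissues. Section 6.3 coregisters the images and has ROI locations cross-checked. That makes locations comparable but does not distinguish a tissue-dependent HU error from shading. The subgroups in Sections 9.4.2 and 9.4.6.1 are anatomical site, patient size and CBCT system.

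**The concern.** Suppose a CBCT image is spatially uniform but compresses the HU scale. The adipose error then differs from the soft-tissue error at every location, and a range pooled over both tissues records that difference as artifact amplitude. If the two CBCT types differ in HU scale, the metric differs between them even when shading is the same.

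At stake is what a positive result means. Artifact amplitude is listed beside CT number error and CNR, with its own hypothesis. A contrast-scale error already enters CT number error, and it enters CNR through the soft-minus-adipose difference in the numerator. One physical change could move all three primary metrics, and a fall in artifact amplitude would not show fewer artifacts. In the other direction, if the grid scan had the larger tissue-dependent error, a true reduction could be hidden.

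**Working it through.** **Plan's own figure.** There is none to reproduce. Section 9.2 sizes the study on the ICC and gives no effect size or variance for artifact amplitude.

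**Inputs from the documents.** The definitions above; 32 photon and 10 proton pairs, analysed separately (Sections 9.2, 4.1 and 9.4.1); log transform; mixed model. With two scans per patient the mixed model matches a paired t test on the logs: on one simulated data set both gave a statistic of -4.96.

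**Assumed inputs.** Five ROIs per tissue; reference values of +40 HU (soft) and -100 HU (adipose); HU scale compressed about 0 HU by 20% in the standard scan and 5% in the grid scan, or 10% versus 0%; shading SD 5, 10 or 20 HU; common offset 0, -30 or -50 HU; two-sided 5% test. Section 9.4.2 does not state sidedness.

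**Model.** Signed ROI error e = offset - c × (reference HU) + shading, where c is the compression.

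**Hand check 1: no shading, no offset.**
- Standard scan: soft -0.20 × 40 = -8; adipose -0.20 × (-100) = +20. Written rule: 20 - 8 = 12 HU.
- Grid scan: soft -2, adipose +5. Written rule: 5 - 2 = 3 HU.
- With signed errors: 20 - (-8) = 28 versus 5 - (-2) = 7 HU.

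Neither image has any spatial non-uniformity.

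**Hand check 2: identical shading of -30, -15, 0, 15 and 30 HU in each tissue.** The grid scan has no tissue error; the standard scan has -8 (soft) and +20 (adipose).
- Common offset -50 HU. Grid errors run from -80 to -20, so the written rule gives 80 - 20 = 60. Standard errors run from -88 to 0, so it gives 88. Apparent reduction: (88 - 60)/88 = 32%. The range within each tissue is 60 in both scans.
- No offset. Grid absolute errors run from 0 to 30, so 30. Standard absolute errors run from 5 to 50, so 45. Splitting by tissue but keeping absolute values gives soft 38 - 7 = 31 and adipose 50 - 5 = 45, mean 38, against 30 for the grid. The signed range within each tissue is 60 in both scans.

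The second case shows that splitting by tissue is not enough when errors straddle zero.

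**Simulation.** The entries are the percentage of trials with a significant reduction favouring the grid (nominal 2.5%), at n=32, with equal shading SD drawn independently for each scan. Repeat runs moved the mid-range figures by up to about three points.

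| Compression | Offset (HU) | Metric | SD 5 | SD 10 | SD 20 |
|---|---|---|---|---|---|
| 20% vs 5% | 0 | as written | 100 | 100 | 75 |
| 20% vs 5% | -30 | as written | 100 | 100 | 19 |
| 20% vs 5% | -50 | as written | 100 | 100 | 70 |
| 10% vs 0% | 0 | as written | 100 | 84 | 13 |
| 10% vs 0% | -30 | as written | 100 | 86 | 3 |
| 20% vs 5% | 0 | signed, pooled | 100 | 100 | 83 |
| 20% vs 5% | 0 | absolute, within tissue | 99 | 99 | 65 |
| all settings tried | | signed, within tissue | 2-3 | 2-3 | 2-3 |

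For 20% versus 5% with no offset, the geometric mean grid/standard ratios under the written rule are 0.47, 0.63 and 0.82; equal shading should give 1.0. At n=10 the same setting gives 100%, 94% and 29%. If both scans of a pair share the same shading pattern (plus 2 HU of ROI noise), the 75% becomes 99%.

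**Pooling in isolation.** At a common offset of -50 HU and SD 10 HU (20% versus 5%, n=32), the pooled absolute range gives 100% and the within-tissue absolute range about 2.5%.

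**The case against.** The strongest reply is that the protocol may define its metric as it likes. It chose the spread of CT number errors across ROIs, and the shading shown in the Fig. 2 caption of Section 2.1 is a phantom illustration, not a limit on what counts as artifact. A smaller soft-versus-adipose error is a gain in quantitative accuracy, and Section 9.4.1 concludes only that visualization and quantitative accuracy would potentially be improved. This is a pilot that reports CT number error and CNR alongside.

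Part of this stands. A fall in the pooled metric may reflect a real grid benefit, so calling every such result false would go too far. It would still be a benefit of contrast scale, reported under a separate hypothesis about artifacts.

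The second reply is that every driving input is assumed. That also stands. The photon comparator already carries a conventional antiscatter grid (Section 6.1.1), so the HU-scale difference there may be modest. When shading dominates, the effect can shrink to the nominal level: 3% at 10% versus 0%, -30 HU and SD 20 HU.

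The third reply is that two faults are mixed. They are, and the table separates them: pooling inflates the claim rate even with signed errors, and the absolute value inflates it even within tissue when errors straddle zero.

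**Conclusion.** The definition does not isolate artifact. With identical shading, a difference between CBCT types in soft-versus-adipose HU error changes the metric. A significant cohort result could then not be attributed to artifact and would overlap with the other two primary metrics.

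Under the assumptions listed, the chance of a significant reduction at n=32 runs from essentially nominal (3%) to 100%. It depends on the HU-scale difference, the shading spread and the common offset, none of which the documents give.

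A reader might infer that the trial will report a spurious artifact reduction, or that the grid's benefit would be illusory. The documents support neither: they do not show that the two scans differ in HU scale, nor in which direction. Nor does the point concern a single scan pair, since significance belongs to the cohort test. This is an inexpensive improvement to a primary metric and does not invalidate the primary analysis.

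**What to change.** In Section 9.4.1, define artifact amplitude from signed ROI errors (CBCT mean HU minus CT mean HU). For each scan, take the maximum minus minimum separately over the soft-tissue ROIs and over the adipose ROIs, then average the two ranges. Use that single value per scan in the Section 9.4.2 model. State there that the averaging over ROIs does not apply to this metric, which has one value per scan. Keep the absolute error for the CT number error metric, and report the pooled range as supportive.

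The word signed must be explicit. Splitting by tissue while keeping Section 9.4.1's absolute errors leaves most of the problem when there is no offset.

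The cost is a short definition with the same scans and the same ROIs. Each range rests on fewer ROIs and is slightly noisier. At least two ROIs per tissue are needed, at the same locations in both scans of a pair.

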## 2.2 BACKGROUND

In preliminary studies, we showed that CBCT images acquired with 2D grid can substantially improve image quality and dose calculation accuracy. Below is the summary of our findings.

**The evaluation of 2D antiscatter grids in phantom (objects that mimic human anatomy) imaging experiments:** We developed numerous 2D grid prototypes, installed them in a clinical CBCT system, and evaluated their effect on image quality in phantom experiments [1, 2, 5, 8, 9]. A significant improvement in image quality was observed, as summarized below.

- We observed that 2D grids can improve contrast-to-noise ratio (CNR) by a factor of two in pelvis sized phantoms, when compared to CBCT images acquired without a 2D grid. Improvement in CNR implies that soft tissue visualization can be improved, which is essential for monitoring shape and location changes of tissues throughout the course of radiation treatment.
- Hounsfield Unit (HU) accuracy of soft-tissue like structures was in the in the order 20 HU, and image artifacts were significantly reduced when compared to CBCT images acquired without a 2D grid. These results also indicate that image intensity and texture features (radiomics features) can be more consistent and reproducible in CBCT images acquired with a 2D grid.

**Accuracy of radiation dose calculations using CBCT images acquired with a 2D grid:** We observed that dose calculation errors in CBCT images acquired with 2D grid are within 2-3%, when compared to dose calculations in gold standard MDCT images [4]. These results indicate that CBCT-based dose calculations may be feasible for CBCT-based treatment plan modifications.

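### Artifact amplitude, a primary metric, is written as the range of absolute CT number errors, so a change in mean HU offset can register as a change in artifact

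*Combined protocol and SAP*

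**What the plan says.** Section 9.4.1 (Study #1) sets out the primary metrics: "Three image quality metrics will be extracted from each CBCT scan; absolute CT number error, image artifact amplitude, and contrast to noise ratio (CNR"). It first defines the error for an ROI: "CT number error is defined as the absolute difference in mean HU values between the CBCT and the gold standard CT images". The next sentence builds the second metric on that term: "Artifact amplitude is defined as the difference between the maximum and minimum value of CT number errors extracted from ROIs" in a scan. The number of ROIs is not fixed. The text says only that "multiple ROIs will be placed primarily in the soft tissue and adipose sections of the imaged anatomy".

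Section 9.1 expects the grid to give "significantly lower CT number errors and artifact amplitudes when compared to standard clinical CBCT scans". In Section 9.4.2, "these values will be log transformed (natural logarithms) for the validity of normality", and a linear mixed model with a random patient effect compares the two scan types. Artifact amplitude is named again in Sections 3, 4.2, 9.1 and 9.4.2. None of these, nor the subgroup plan in 9.4.6.1, gives a signed formula or any other definition.

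**The concern.** Artifact amplitude is meant to capture how unevenly HU errors are distributed across a scan. Shading can make some regions too dark and others too bright. Taking absolute values first folds the dark and bright errors onto the same side of zero, so part of the spread between them disappears before the range is taken.

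How much disappears depends on where the scan's errors are centred. A scan whose errors all lie well below zero loses nothing. A scan centred near zero loses a large share. If the grid brings HU values closer to the reference, which is one way the CT number error hypothesis could come true, its scans are folded more than the standard scans. A pure offset correction, already credited under CT number error, would then be credited again as artifact reduction. The pairing of scans within a participant does not remove this, because the two scans have different offsets.

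**Working it through.** The plan gives no effect size, SD or expected value for artifact amplitude, so there is no stated figure to reproduce. The check applies the written definition literally and compares it with the signed range.

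**Notation.** For ROI i, d_i = mean HU(CBCT) - mean HU(reference CT). Signed range: A_sgn = max(d_i) - min(d_i). As written: A_abs = max|d_i| - min|d_i|.

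**Algebra.** If all d_i share one sign, A_abs = A_sgn. If signs are mixed, let M = max(d_i) > 0 and m = min(d_i) < 0. Then A_sgn = M + |m| and A_abs = max(M, |m|) - min|d_i|. The shortfall is A_sgn - A_abs = min(M, |m|) + min|d_i|, which is always positive.

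Example with assumed errors -60, -20, +20, +60 HU: A_sgn = 60 + 60 = 120. The shortfall is 60 + 20 = 80, so A_abs = 40.

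**Simulation inputs (all assumed).** Independent normal ROI errors, 10 ROIs per scan, at least 100,000 simulated scans per setting. The only HU scale in the documents is the phantom result in Section 2.2, "Hounsfield Unit (HU) accuracy of soft-tissue like structures was in the in the order 20 HU", and it serves only to pick a plausible order of magnitude.

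**Case 1: the grid only re-centres.** Standard mean -60, SD 20; grid mean 0, SD 20.
- Mean signed range: 61.5 HU standard, 61.6 HU grid. Ratio 1.00, so there is no change in non-uniformity.
- Mean as-written value: 61.4 HU standard, 35.3 HU grid. Ratio 35.3/61.4 = 0.575, a false reduction of about 42%.
- On the geometric-mean scale, which the log-transformed model targets, the ratio is 0.57. It stays at 0.56 to 0.57 for 4 to 20 ROIs.

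**Case 2: real benefit, overstated.** Standard mean -40, SD 40; grid mean 0, SD 20.
- Signed: 61.6/123.2 = 0.50.
- As written: 35.3/94.2 = 0.375, or about 0.38.

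**Other settings (grid/standard ratio, 10 ROIs).**

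| Standard mean, SD | Grid mean, SD | Signed | As written |
|---|---|---|---|
| 0, 40 | 0, 20 | 0.50 | 0.50 |
| -100, 20 | -60, 15 | 0.75 | 0.75 |
| -60, 20 | -20, 10 | 0.50 | 0.48 |
| 0, 30 | -60, 20 | 0.67 | 1.16 |

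The first row shows that equal centring at zero protects the ratio, although each as-written value is 1 - 35.3/61.6 = 43% below its signed range. The next two rows show little or no bias when nearly all errors share a sign. The last row shows that the direction can reverse, but only with the larger offset placed on the grid scan.

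**ROI count.** The expected signed range of normal errors is about 2.5 SD with 6 ROIs, 3.1 SD with 10 and 3.7 SD with 20. A range, signed or not, therefore grows with the number of ROIs.

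**The case against.** The strongest reply is that signed errors were intended. The first metric is repeatedly called absolute CT number error, while the amplitude sentence drops the word absolute, and a maximum-minus-minimum artifact measure reads naturally as a signed range. That may be so. But the term it uses was defined as absolute one sentence before, and nothing else in the plan overrides that. Two analysts could compute different primary results from the same ROIs, so the text needs correcting under either intent.

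Other limits stand and narrow the point:
- A reader might infer that the metric does not measure non-uniformity at all. That goes too far: it equals the signed range when errors share one sign, and the ratio between scans is preserved when both are centred at zero.
- A reader might infer that the trial could well report a benefit as a harm. Reversal is arithmetically possible, but it needs the grid to have the larger offset or an unusual sign pattern. That runs against Section 9.1, the phantom accuracy in Section 2.2, and the shading suppression described with Fig. 2 in Section 2.1.
- A reader might worry that an amplitude of zero breaks the log transformation. This needs exactly equal absolute errors in every ROI, which has essentially zero probability with continuous ROI means.
- ROI count is a separate matter. Section 6.3 coregisters all of a participant's images, makes ROI locations comparable and adds a second-person check, which largely protects the paired comparison. Comparisons between subgroups remain exposed.
- CT number error and CNR are unaffected, and this is a pilot.

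**Conclusion.** The concern holds as a defect in the written definition of one of the three primary metrics. When ROI errors have mixed signs, the as-written amplitude understates the spread by an amount tied to the scan's mean HU offset, so a difference in offset between scan types can bias the comparison. Under the stated assumptions, the bias favours the grid where the grid moves HU values towards the reference: a false reduction of about 42% with identical spread, or 0.38 in place of 0.50 where there is a real benefit.

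These sizes rest on assumed normal ROI errors, assumed means and SDs, and 10 ROIs. The documents do not give the sign pattern of ROI errors, so the actual bias could be negligible. They support neither a claim that the comparison will be biased nor one that it will be reversed.

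**What to change.** In Section 9.4.1:
- Define the signed error for each ROI as e = mean HU(CBCT) - mean HU(reference CT).
- Keep the mean of |e| over ROIs as the CT number error metric.
- Define artifact amplitude as max(e) - min(e) of the signed errors, using the same ROI set in both scans of a participant.
- For comparisons between subgroups (Section 9.4.6.1), use a common ROI count or replace the range with the SD of e, because the range grows with the number of ROIs.

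The core change is one sentence. It uses the same ROIs and the same ROI means, so it needs no new data or scans. It should be made before the metric is computed, so that the choice between signed and unsigned errors is not made after seeing results.
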